The "repetition-cue-reward" model of habit formation has obvious applicability to medication taking, which is a daily repetitive activity. Existing evidence supports the benefits of reminder cues for adherence, such as those using text messaging, as well as rewards in the form of copayment elimination or daily lotteries. However, medication adherence has notable differences. For example, consistently taking preventive medications seldom have obvious symptomatic benefits, particularly short-term benefits that patients can easily attribute to the medications themselves. Further, context cues, such recommending that patients put their medications beside their toothbrush or coffee pot, are insufficient to motivate behavior change for many, and thus more effective tailoring or more potent strategies need to be developed. Accordingly, we plan to adapt the "cue-reward" methodology to improve adherence to rheumatic disease medications.

PI: [name] Version 16. October 10, 2022

Specific Aims

This pilot aims to evaluate the feasibility and effectiveness of using the repetition-cue-reward model of healthy habit formation to improve medication adherence in patients with arthritis and rheumatic disease. To accomplish this Aim, this project consists of two phases. This present protocol focuses only on the second phase, which consists of a small, pragmatic randomized clinical trial. Due to the current COVID-19 related concerns, this study can be conducted entirely virtually until system-wide policies allow in-person study visits to resume or if the patient does not feel comfortable with in-person study visits.

This phase has the following Aim: "To determine whether strategies that couple context cues and rewards improve adherence to medications." We will conduct a 3-arm randomized controlled trial to determine the feasibility, acceptability and effectiveness of motivating consistent medication use with the application of the cue-reward model of habit formation.

The overarching goal of this phase is to understand what context cues and rewards can be used to help patients form long-lasting healthy habits, such as taking their medication(s). By conducting this randomized control trial, we will test potential cues and rewards that can be leveraged to positively impact medication-taking behavior in patients with arthritis and other rheumatic diseases.

Subject Selection

Phase 2: Randomized controlled trial

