[figure not shown]

Statistical/Programming Plan for Cue Reward Trial Analysis

Protocol Version Date: 2022-12-16

- 1. Title:** Medication Adherence Patterns in Rheumatic Diseases: A Behavioral Trial: Phase 2 trial results
- 2. Core research team**
PI: [name]; Co-PI: [name]
- 3. Aim(s): To determine whether strategies that couple context cues and rewards improve adherence to medications**
- 4. Data source:**
 - a) REDCap data for 56 consented patients (20 = in Adaptive intervention; 18 = in Non-Adaptive Intervention; 18 = in Control) – one dataset
 - b) Pillsy pill bottle adherence data for 56 patients - there are N= 352 daily 000_Pillsy files spanning the length of the trial
 - c) IRB: 2020P003826
 - d) NIA (NIH) funded P30

5. Overall trial diagram:

6. Cohort Identification

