6.2.2 Specify inclusion criteria for cohort entry and define the index date

Patients are already identified by their study ID (56 patients altogether). The index date is the first day of intervention (“start_date” in REDCap).

7. Variables

7.1 Exposure-related variables:

Patient-level cohort: Within this cohort, please measure and provide the following variables at the patient level:

a) Using the **REDCap file:**

- Patient demographics:
 - Age (age_years, age), numeric. Please also calculate using dob and start_date
 - Sex (sex)
 - 0 = Not listed
 - 1 = Female
 - 2 = Male
 - Sex if Sex is not listed (sex_other)
 - Race/ethnicity (self reported)
 - 1 = White
 - 2 = Black or African American
 - 3 = American Indian/ Alaska Native
 - 4 = Asian
 - 5 = Native Hawaiian or Other Pacific Islander
 - 6 = Hispanic/Latinx
 - Education level (education)
 - 1 = Less than high school diploma
 - 2 = High school diploma
 - 3 = Some college
 - 4 = College degree
 - 5 = Graduate degree
 - Marital status (marital)
 - 1 = Married
 - 2 = Living with partner/ Domestic partnership
 - 3 = Widowed
 - 4 = Divorced/ Separated
 - 5 = Never married/ Single
 - Employment Status (employment)
 - 1 = Employed
 - 2 = Job seeking

- 3 = Not job seeking
- 4 = Retired
- 5 = Disabled
- Income (self-reported) (income)
 - 1 = Less than \$20,000
 - 2 = \$20,000 to \$34,999
 - 3 = \$35,000 to \$49,999
 - 4 = \$50,000 to \$74,999
 - 5 = \$75,000 to \$99,999
 - 6 = Over \$100,000
 - 7 = Prefer not to say
- Number of self-reported medications on a daily basis (num_meds_daily)
- Number of self-reported medications on a weekly basis (num_meds_weekly)
- Recruitment method (rec_type)
 - 1 = PCP
 - 2 = Rheumatology
- Baseline Uric acid (ua_baseline) used for the study, numeric
- Baseline Uric acid date (ua_baseline_date)
- Baseline Uric acid stratum (ua_stratum)
 - 1 = 6-8 mg/dl
 - 2 = >8 mg/dl
- Arm (arm):
 - 0 = Control,
 - 1 = Non-adaptive intervention,
 - 2 = Adaptive intervention
- Number of prescribed study medications (bottles), numeric
- Medication names (bottle_1_med, bottle_2_med, bottle_3_med)

7.2 Baseline Medication Use Questionnaire:

- 3-item questionnaire: Please perform a linear transformation of the following three variables to a scale of 100 and take the mean of the three for each patient, for those with baseline survey data:
 - missed_doses: numerical value, 0-30. For each day missed, calculate the percentage of days taken out of 30 (e.g. missed_doses=2 → 28/30 = 93.33)

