1. Aggregate adherence (adh_daily) into the mean daily adherence value for each patient (ranging from 0 to 1) for the **18 weeks** from “start_date” to the end of follow up (if date range is less than 18 weeks, calculate just for the respective date range) → label this as “adherence_primary_outcome”
2. Repeat the aggregation of adherence for each patient omitting the first 7 days of data (i.e., index date → index date+7)
3. Repeat the aggregation of adherence for each patient omitting the first 14 days of data (i.e., index date → index date+14)
4. Repeat the aggregation of adherence for each patient, but censor patients in the adherence calculation at the time they have stopped using the electronic pill bottle for >30 days (defined as “adh_daily”=0 for >30 consecutive days in Pillsy data)
 - Please generate a flag for the patient (1/0) and provide the date in which they were censored if this occurs (leave the date as missing if does not occur)
5. Repeat the aggregation of adherence for each patient for the **12 weeks** from “start date” to the “intervention_date” (the intervention completion date) or “withdraw_date”, whichever is earlier.
6. Repeat the aggregation of adherence (adh_daily_allopurinolqd) for 18 weeks from “start_date” to the end of follow up for Allopurinol QD – label as “adh_allopurinol”.

d) Use generalized linear models (proc genmod) to compare nonadaptive vs. control and adaptive vs. control; calculate unadjusted mean differences for these groups and adjusted mean differences (adjusted for age, sex, race/ethnicity). The link=identity and dist=normal). Recruitment type (PCP vs. rheumatology) also accounted for in the model.

B) Uric acid level outcomes (Change in uric acid levels – Exploratory outcome)

a) Using the **REDCap file**:

- Please measure the difference between “ua_end” (outcome) and “ua_baseline” (baseline).
- Please provide the dates for both “ua_date_end” and “ua_baseline_date”
- Please provide a flag if missing “ua_end” (outcome)

b) Use generalized linear models (proc genmod) to compare nonadaptive vs. control and

adaptive vs. control; calculate unadjusted mean differences for these groups and adjusted mean differences (adjusted for age, sex, race/ethnicity). The link=identity and dist=normal). Recruitment type (PCP vs. rheumatology) and baseline uric acid level also accounted for in the model.

C) Self-Reported Outcomes:

- Automaticity scores (automaticity): automaticity_1_end to automaticity_4_end.
 - 0=No
 - 1=Yes

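### The SAP's PROC GENMOD normal model, run at its defaults with 56 patients, gives error bars that are too narrow: an assumed 5% test runs at 6.2–6.5% unadjusted and 7.3–8.6% adjusted

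*SAP*

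**What the plan says.** SAP section 8.A.d gives the primary analysis of mean daily adherence: "Use generalized linear models (proc genmod) to compare nonadaptive vs. control and adaptive vs. control". It asks the programmer to "calculate unadjusted mean differences for these groups and adjusted mean differences (adjusted for age, sex, race/ethnicity"), and continues: "The link=identity and dist=normal). Recruitment type (PCP vs. rheumatology) also accounted for in the model". Section 8.B.b repeats the procedure for change in uric acid, labelled exploratory, with one more covariate: "Recruitment type (PCP vs. rheumatology) and baseline uric acid level also accounted for in the model".

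Section 4 gives the sample as "REDCap data for 56 consented patients", split 20 adaptive, 18 non-adaptive and 18 control. Section 8.A.c reduces each patient's daily record to one mean, over a shorter period if follow-up is short, so the model has 56 observations. Section 7.1 lists six race/ethnicity codes, the last being "6 = Hispanic/Latinx".

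Neither document states an alpha level, a confidence interval method, a variance estimator or a reference distribution for the tests.

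**The concern.** A normal model with identity link is an ordinary linear regression, for which exact small-sample inference exists: residual variance RSS/(n−p) and a t distribution on n−p degrees of freedom. PROC GENMOD with a normal distribution does not use it by default. It takes the maximum-likelihood variance RSS/n and refers the Wald statistic to the normal distribution. Both departures make the intervals narrower and the p-values smaller, and the effect grows with the number of fitted parameters p. With 56 patients and up to 11 parameters it is not negligible.

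At stake is the stated precision of the two arm-versus-control contrasts in adherence and in uric acid. The adjusted contrasts suffer more, because they spend more parameters. The point estimates do not change. The SAP gives this model for adherence and uric acid only, so the point does not extend to the questionnaire outcomes.

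**Working it through.** The documents contain no alpha, power or sample-size figure, so there is no stated number to reproduce first.

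**Inputs**
- n = 56 (SAP section 4), one value per patient (SAP 8.A.c).
- Two-sided 5% level: assumed, z = 1.96.
- p unadjusted: intercept plus two arm terms = 3. The text does not say whether recruitment type also enters the unadjusted model; if it does, p = 4.
- p adjusted: 4 + age (1, linear) + sex (1, taken as two levels) + race/ethnicity (1 if it falls into two groups, 5 if all six codes occur) = 7 to 11. The documents give no race distribution.

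**Formulas.** The default Wald statistic equals a t statistic on n−p degrees of freedom multiplied by √(n/(n−p)). Hence:
- true size = 2·P(t[n−p] > 1.96·√((n−p)/n))
- interval width relative to the t interval = 1.96·√((n−p)/n) / t[.975, n−p]
- printed p-value when the correct one is 0.050 = 2·P(Z > t[.975, n−p] / √((n−p)/n))

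**Worked example, p = 7.** There are 49 degrees of freedom and √(49/56) = 0.9354. The effective critical value on the t scale is 1.96 × 0.9354 = 1.833, where 2.010 is needed. Size = 2·P(t[49] > 1.833) = 7.28%. Width ratio = 1.833/2.010 = 0.912. Printed p-value = 2·P(Z > 2.010/0.9354) = 0.032.

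**Results, n = 56**

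| p | Model | True size | Width ratio | Correct p of 0.050 prints as |
|---|---|---|---|---|
| 3 | unadjusted, arms only | 6.20% | 0.951 | 0.039 |
| 4 | unadjusted, with recruitment type | 6.45% | 0.941 | 0.037 |
| 7 | adjusted, race in two groups | 7.28% | 0.912 | 0.032 |
| 8 | adjusted | 7.58% | 0.903 | 0.030 |
| 9 | adjusted | 7.90% | 0.893 | 0.028 |
| 10 | adjusted | 8.23% | 0.883 | 0.026 |
| 11 | adjusted, six race codes | 8.57% | 0.872 | 0.025 |

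Coverage of a nominal 95% interval is 100% minus the size: 93.5–93.8% unadjusted and 91.4–92.7% adjusted.

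**Simulation check.** With 200,000 null trials per model, arms of 18/18/20, normal errors and an assumed covariate mix, the default inference rejected 6.2% (p = 3), 6.4–6.5% (p = 4), 7.3–7.4% (p = 7) and 8.6–8.7% (p = 11). RSS/(n−p) with a t reference rejected 5.0–5.1% throughout. A separate run of 100,000 replicates with bounded, skewed Beta(2,1) errors gave 6.1–6.2%, 6.5%, 7.3% and 8.9% at p = 3, 4, 7 and 12, so the result does not depend on exactly normal adherence data.

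**Correcting the scale only.** With RSS/(n−p) but a normal reference, the size is 2·P(t[n−p] > 1.96), which is 5.53% at p = 3 and 5.62% at p = 11.

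**Uric acid (8.B.b).** Baseline uric acid adds one parameter to the adjusted model, so p = 8 to 12. With complete data the size is 7.6% to 8.9%. It rises if values are missing: with an assumed n = 40 it would be 8.9% to 11.2%.

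**The case against.** **No test is requested.** The SAP asks for mean differences, and Table 2 has no column for intervals or p-values. No named output is wrong, and a type I error rate needs an alpha that nobody set. The facts are right, and they are why the 5% level is labelled an assumption. But the aim in SAP section 3 is to determine whether the strategies improve adherence, and 8.A.d tells the programmer to compare arms. That needs a measure of uncertainty, and this model is the only source the SAP offers.

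**The default is not SAP text.** The SAP is silent on options and does not forbid a different scale or a t reference. True, but it names the procedure, with "The link=identity and dist=normal", and overrides nothing, so a programmer following it gets the defaults.

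**The adjusted range is not a bound.** This stands. SAP 7.1 has three sex codes; if all occur with all six race codes, p = 12 and the size is 8.9%. Conversely, p = 11 needs every race code to occur among 56 patients. Fitting each contrast on two arms only (n = 36 or 38) would give 6.4–6.5% at p = 2 and 8.2–10.8% at p = 6 to 10.

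**The remedy assumes equal variances.** This also stands as a limit. With an assumed adaptive-arm SD of 0.7 times the others, a simulated pooled t test at p = 3 rejected 7.6% for non-adaptive versus control and 4.2% for adaptive versus control. The SAP's own model makes the same assumption, so this does not favour the default inference.

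**It is a pilot.** The Protocol's Specific Aims describe a phase "which consists of a small, pragmatic randomized clinical trial", and the excess is modest. That limits the severity. A small sample is also exactly where the approximation fails.

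**Conclusion.** The concern holds, and the plan is wrong as written on this point. Run at its defaults on 56 patients, the named procedure gives standard errors, intervals and p-values that are too optimistic. Per contrast, a nominal 5% test runs at 6.2–6.5% unadjusted and 7.3–8.6% adjusted; 95% intervals are 4.9–5.9% and 8.8–12.8% too narrow.

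These figures assume a two-sided 5% level, all three arms in one model, equal-variance normal errors, age entered linearly, two sex levels, and between two and six race/ethnicity groups. The uric acid figures also assume complete data.

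This should be fixed, but it is a modest error in a small pilot and leaves the estimated mean differences intact.

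**What to change.** Add one line to SAP 8.A.d: fit the same linear model with residual variance RSS/(n−p), and report 95% confidence intervals and p-values from the t distribution on n−p degrees of freedom. PROC GLM does this directly. GENMOD with SCALE=DEVIANCE or SCALE=PEARSON also works if the t reference is added; the SCALE= option alone does not complete the correction. State the alpha level in the same place. Apply the same inference in 8.B.b, with n set to the patients who have the uric acid values the model needs.

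The covariates need not change, no new data are required, and the point estimates stay the same. The cost is wider intervals: about 5–6% unadjusted (1/0.951 = 1.05; 1/0.941 = 1.06) and 10–15% adjusted (1/0.912 = 1.10; 1/0.872 = 1.15). Under the SAP's normal model that is the width 95% coverage requires.

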Please confirm receipt of this email and indicate if your preference is to NOT receive secure emails from me at this time. If I do not hear back from you, then all future emails will be sent either via patient gateway or via secure messaging as is MGB policy."

Patients who prefer to correspond via email and to complete surveys electronically, will have the option to do so securely via the above channels for email and via REDCap, with all links sent securely as well.

PI: [name]

Version 16. October 10, 2022

Study Procedures

Participants will have 3 study-related visits. These study visits can be completed completely virtually or in-person during clinic visits (if/when COVID-19 precautions are lifted). To cover both possible time windows, both sets of procedures are described in further detail below.

Using a random number generator, the study research assistant will randomize 20 patients to the first intervention arm, 20 patients to the second intervention arm, and 20 patients to the control arm. Other clinic staff and analysts will be blinded to arm assignment. A password-protected, REDCap database will link study-specific ID and participant name.

Study Procedures

1st Virtual Study Visit

At the first study visit conducted using a Partners approved video platform, subjects will provide written informed consent for all study procedures, including the use of text messages, and be enrolled into the study. The study staff will be virtually present for the consent process and will obtain electronic informed consent from the participant using Partners approved REDCap e-consent/paperless consent process.

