 - medication_supposed :
 - 1=Never → 0
 - 2=Rarely → 20
 - 3=Sometimes → 40
 - 4=Usually → 60
 - 5=Almost Always → 80
 - 6=Always → 100
 - meds_good_job:
 - 1=Very Poor → 0
 - 2=Poor → 20
 - 3=Fair → 40

- 4=Good → 60
- 5=Very Good → 80
- 6=Excellent → 100
- Please generate a flag for missing any one of these fields (missed_doses, medication_supposed, meds_good_job)
- Automaticity score categories (automaticity): Present the scores for the 4 questions – automaticity_1_end to automaticity_4_end.
 - 0=No
 - 1=Yes
- Routine related questionnaire
 - Score the following from 1 (Not at all) to 7 (Very much so): routine, same_time, continue_way, take_same_place, take_right_before, take_water, take_same_cup, keep_same_place
- Perception related questionnaire
 - Score from 1 (Strongly Disagree) to 5 (Strongly Agree) the following: regular_apts, tx_plan_difference, med_help_control, prescribed_take_daily, not_taking_effect, feel_well_stop, live_long, control_gout, gout_better_worse, actions_effect

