- Routine related questionnaire
 - Score the following from 1 to 7: routine_end, same_time_end, continue_way_end, take_same_place_end, take_right_before_end, take_water_end, take_same_cup_end, keep_same_place_end
- Perception related questionnaire
 - Score from 1 (Strongly Disagree) to 5 (Strongly Agree) the following: regular_apts_end, tx_plan_difference_end, med_help_control_end, prescribed_take_daily_end, not_taking_effect_end, feel_well_stop_end, live_long_end, control_gout_end, gout_better_worse_end, actions_effect_end

D) Feasibility Outcomes:

- Score from 1 (Strongly **agree**) to 5 (Strongly **disagree**) the following: cue_useful, cue_text_useful, reward_text_useful

Requested Results:

Table 1: Baseline characteristics

	Usual Care	Non-adaptive	Adaptive
N, (%)			
Age (Mean, SD) (Median, IQR)			
Female (N, %)			
Partnered/ Marital status Married Living with partner/ Domestic partnership Widowed Divorced/ Separated Never married/ Single			

Race White Black or African American American Indian/ Alaska Native Asian Native Hawaiian or Other Pacific Islander Hispanic/Latinx			
Education level Less than high school diploma High school diploma Some college College degree Graduate degree			
Employment Employed Job seeking Not job seeking Retired Disabled			
Baseline Uric acid (mg/dL)			
Medication Use Baseline Automaticity score (Mean, SD) Routine Perception			
Recruitment method Rheumatology (N, %) PCP (N, %)			
Self-reported medications on a daily basis (Mean, SD)			
Self-reported medications on a weekly basis (Mean, SD)			
Number of prescribed study medications (N, %) 1 2 3			
Baseline self-reported adherence (Mean, SD)			
Disease activity (Mean, SD)			
Number of Pillsy bottles used in the study			

1 2+			
Patients intensified (adaptive arm)			

Table 2: Primary and Secondary Outcomes

	Control Mean (SD)	Non-adaptive intervention Mean (SD)	Adaptive intervention Mean (SD)	Unadjusted absolute difference	Adjusted absolute difference		
				(Non-adaptive vs Control)	(Adaptive vs Control)	(Non-adaptive vs Control)	(Adaptive vs Control)
Primary Outcome:							
Adherence							
Secondary Outcome:							
Change in uric acid levels							
Change in automaticity							
Change in perception							
Change in sense of routine

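### The adjusted primary adherence model leaves out the baseline self-reported adherence score that the SAP already builds: a missed, cheap chance of better precision, not an error

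*SAP*

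**What the plan says.** SAP 8.A.d specifies a normal, identity-link model for mean daily bottle adherence over 18 weeks, to "compare nonadaptive vs. control and adaptive vs. control". The analyst is to "calculate unadjusted mean differences for these groups and adjusted mean differences (adjusted for age, sex, race/ethnicity"), and the SAP adds: "Recruitment type (PCP vs. rheumatology) also accounted for in the model". No baseline adherence term appears.

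SAP 7.2 rescales three baseline survey items "to a scale of 100 and take the mean of the three for each patient, for those with baseline survey data". It expects gaps: "Please generate a flag for missing any one of these fields (missed_doses, medication_supposed, meds_good_job"). The only place the SAP then uses this score is the Table 1 row "Baseline self-reported adherence (Mean, SD"). The documents describe no other measure of adherence before the intervention, because bottle adherence is counted from the index date.

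The exploratory uric acid model in SAP 8.B.b is otherwise the same, but has "baseline uric acid level also accounted for in the model".

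On timing, the Protocol's Study Procedures say that "the study research assistant will randomize 20 patients to the first intervention arm", and likewise for the other arms, without placing this step before or after the baseline survey. Under the 1st Virtual Study Visit, patients get a survey link to complete when it suits them, and bottles are mailed after that visit. In Arms A and B a charity sticker goes under the cap. SAP 6.2.1 lists mailing, consent, start and intervention-completion dates, but no survey or randomisation date.

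**The concern.** The trial has 56 patients, 18 to 20 per arm, so intervals on the adherence differences will be wide and no more patients can be added. Past adherence is a natural candidate predictor of later adherence, and the score is already being programmed. Six-level race/ethnicity may take up to 5 degrees of freedom in the planned model; the score would take 1. If the score predicts bottle adherence beyond the planned covariates, leaving it out gives away precision that costs almost nothing to obtain.

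Two things limit the benefit. The correlation may be weak: the outcome is bottle opening, not self-report, and it includes zero days after a patient stops using the bottle, which SAP 8.A.c.4 handles only in a repeat analysis. And the score is safe to adjust for only if it was given before the patient could know the arm.

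**Working it through.** The documents give no SD, effect size, power or correlation, so there is no plan figure to reproduce. The check asks how large r must be before one added covariate pays for itself.

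**Inputs**
- Arm sizes (SAP 4): 18 control, 18 non-adaptive, 20 adaptive.
- Planned terms (SAP 8.A.d): age 1 df, sex 1, race/ethnicity 5 (six levels), recruitment type 1.
- r, assumed: within-arm partial correlation of score and outcome given those covariates.
- m, assumed: share of scores missing and filled with the overall mean.

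**Residual df before adding the score (ν)**
- One three-arm model: 56 − (1 + 2 + 1 + 1 + 5 + 1) = 45.
- Two two-arm models: 36 − (1 + 1 + 1 + 1 + 5 + 1) = 26 and 38 − 10 = 28.

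**Formulas**
- Variance ratio (with score / planned) ≈ [1 − r²(1 − m)] × (ν − 1)/(ν − 2). The second factor is the cost of chance imbalance in the score.
- Approximate break-even: r = √{1/[(ν − 1)(1 − m)]}.

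**Break-even with complete scores**
- Three-arm: √(1/44) = 0.151.
- Two-arm: √(1/25) = 0.200 and √(1/27) = 0.192.

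**Break-even with missing scores**
- Three-arm formula: 0.151/√0.9 = 0.159 at 10%, 0.151/√0.8 = 0.169 at 20%, 0.151/√0.6 = 0.195 at 40%.
- Simulation (20,000 designs, arms 18/18/20, assumed race mix 70/12/1/7/1/9%): three-arm 0.158, 0.168, 0.194; two-arm 0.204, 0.217, 0.249.

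**Variance ratio by simulation, 10% / 20% missing**

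| r | One three-arm model | Two two-arm models |
|---|---|---|
| 0 | 1.023 / 1.023 | 1.039 / 1.038 |
| 0.2 | 0.986 / 0.991 | 1.001 / 1.006 |
| 0.3 | 0.940 / 0.950 | 0.955 / 0.965 |
| 0.4 | 0.876 / 0.893 | 0.890 / 0.907 |
| 0.5 | 0.794 / 0.820 | 0.806 / 0.833 |

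Formula check, three-arm, r = 0.3, m = 0.1: (1 − 0.09 × 0.9) × 44/43 = 0.919 × 1.023 = 0.940.

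**Interval width** is approximately the square root of the ratio. At r = 0.3, √0.940 = 0.970 and √0.965 = 0.982, so 2-3% narrower. At 0.4, √0.876 = 0.936 and √0.907 = 0.952, so 5-6%. At 0.5, √0.794 = 0.891 and √0.833 = 0.913, so 9-11%. Counting the lost degree of freedom in the t multiplier, and allowing other codings of sex and race, gives break-even at 10% missing of 0.156-0.165 (three-arm) and 0.196-0.225 (two-arm).

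**Heavier loss.** With 40% of scores unusable, the ratios at r = 0.4 are 0.927 and 0.941, a variance gain of about 7% or 6%.

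**Missing indicator.** Adding one raises break-even at 10-20% missing to 0.22-0.24 (three-arm) or 0.28-0.30 (two-arm), so it is not worth having here.

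**Scores given after the arm was known.** If knowing the arm shifted scores by 0.3 SD in one arm (assumed), adjusting at r = 0.3 would move the contrast by 0.3 × 0.3 = 0.09 SD. With an assumed adherence SD of 0.25 that is 0.09 × 25 = 2.25 percentage points. This is a risk of a careless fix, not of the present plan.

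**The case against.** The choice of covariates at this sample size is a design decision. The SAP names its covariates in advance and reports an unadjusted contrast as well. The benefit cannot be sized from the documents, since r is unknown and the score comes from a different instrument. The uric acid comparison is also weaker than it looks: that outcome is a change in one laboratory value, for which baseline adjustment is standard, whereas bottle adherence has no baseline on the same instrument. Changing the model when the SAP already lists data for 56 patients and 352 daily files has a credibility cost, against a gain of perhaps a few percent. And restricting to scores that precede allocation could discard many of them.

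Most of this stands. It keeps the point at the level of an improvement to consider, and it is why the fix has a fallback. It does not remove the point: the score is already requested, the loss if it is uninformative is small, and the planned results stay on the page.

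A reader might infer that the primary comparison is biased or that the SAP contradicts itself. Neither follows: randomisation protects the contrast without the score, and the two models concern different kinds of outcome. A reader might also take 0.16 or 0.20 as the point where adjustment becomes worthwhile, or compare it with a plain correlation. Those values are where the gain is zero, and they refer to the partial correlation; a plain correlation above them may fall short once age, sex, race/ethnicity and recruitment type are in the model. Finally, SAP 8.A.d does not say whether one three-arm model or two two-arm models are fitted. That is missing detail, not a fault, although it decides which thresholds apply.

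**Conclusion.** The point holds as a missed, inexpensive precision improvement. The omission is plain in the text, and the thresholds were reproduced by formula and by separate simulations.

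The likely size is modest. If r is at least 0.3, the gain is a few percent of interval width, reaching about a tenth at 0.5. Below break-even there is a small loss, at most about 2% (three-arm) or 4% (two-arm) of variance. With 40% of scores missing, break-even rises to about 0.19 or 0.25. All of this rests on an assumed r, an assumed missing share, an assumed race mix and scores that truly precede allocation. The documents settle none of these, so confidence that the change would help in practice is medium.

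**What to change.** Add the three-item baseline score to the adjusted model in SAP 8.A.d under these rules:

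- Use only scores completed before the patient could know the allocation.
- Treat as missing any later score, any score whose order cannot be established (for example survey and randomisation on the same day without times), and any score lacking one of its three items.
- Fill missing scores with the overall mean of the usable scores, without a missing indicator, so that all 56 patients stay in the model.
- Request the date and time of survey completion and of randomisation. The start date does not serve, because a patient may have learned the arm before it.
- If most scores cannot be shown to precede allocation, leave the score out.
- Keep the unadjusted and planned adjusted results. Record when the change was made; if outcomes by arm had been seen by then, report the score-adjusted result as a labelled sensitivity analysis.
- State in the same edit whether one three-arm model or two two-arm models are fitted.

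The cost is a short SAP paragraph, one degree of freedom in the score-adjusted model, and two date-time fields. Any loss of precision falls on the score-adjusted result only.
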